6.1.3 Tobacco/Nicotine Product Use History

Subjects will be required to report previous tobacco-product and nicotine-product use histories to satisfy the study inclusion and exclusion criteria.

Details of the subject's OBCC, including the brand, brand style, flavour, cigarette length, and amount of daily use will be recorded at Screening and updated at Check-in as necessary. A colour photocopy or photograph of the subject's OBCC package (including the branding and the UPC code) will be taken by the CRU staff at Check-in.

6.1.4 Exhaled Carbon Monoxide

Exhaled CO levels will be measured using a Bedfont Micro+ Smokerlyzer or similar device, at Screening and at Check-in.

6.2 Check-in and Confinement

Subjects will check in to the CRU on Day --1 at a time specified by the CRU. Check-in procedures will be performed as delineated in the Study Events Flow Chart ([Table 1](#)).

After Check-in, subjects will complete one set of questionnaires for the purpose of familiarisation with subjective effects questions, appropriate use of the VAS, and use of the computerised tablet system. Data collected from the training session will not be used for any analysis.

The clinical team will explain how the [REDACTED] devices will be used. Subjects will have the opportunity to see the products/devices and packaging and will participate in a Product Trial in which they will use the [REDACTED] device by taking 5 puffs from an [REDACTED] tobacco stick and 5 puffs from an [REDACTED] herbal stick with the flavour of their choice. The [REDACTED] stick flavours will be recorded; however, no assessments will be made. The purpose of the Product Trial is to familiarise subjects to the [REDACTED] device and [REDACTED] sticks prior to study assessments. All products/devices used in the trial session will not be used in the clinical study but will be retained as demonstration samples for accountability purposes.

Subjects will have their personal belongings thoroughly checked during Check-in. All subjects will be required to shower and will receive clean articles of clothing prior to the start of each morning controlled product use (i.e., during the 12-hour abstinence) on Days 1, 2, 3, 4 and 5.

Subjects will be confined from Check-in on Day -1 through completion of scheduled study events on Day 5.

A subject may be required to remain at the CRU for longer at the discretion of the Investigator or designee.

6.2.1 Baseline Assessments (Day -1)

Subjects will continue to smoke their OBCC from Check-in (after completion of the Product Trial and check-in procedures) through Day -1, but will abstain from use of any tobacco- or nicotine-containing products for at least 12 hours prior to the start of morning controlled product use session on Day 1.

The number of OBCC smoked per day will be documented.

Baseline assessments will be performed as delineated in the Study Events Flow Chart ([Table 1](#)).

6.3 Product Use (Days 1 Through 5)

On Days 1 through 5, subjects will use the study product they are assigned to use according to the randomisation scheme.

In the morning of each day, subjects will use the assigned study product under controlled conditions by completely using a single unit (one stick, approximately 10 puffs) of the assigned

study product, with puffs taken at 30-second intervals and of 3-seconds duration. Following the 4-hour PK blood collection, subjects will start a 4-hour *ad libitum* product use session (no limits on cigarette or HTP/HHP consumption) with the same study product used during the morning controlled use session.

Each subject will be provided with a new/unused [REDACTED] device for each day of HTP/HHP product use (i.e., the same device will be used for the morning controlled product use session and the *ad libitum* product use session on the same day). Subjects will be provided the assigned HTP/HHP stick (based on randomisation sequence) or OBCC on each day. The clinic staff will document the time each product is dispensed. **The [REDACTED] device should be used on the 'Intense' Mode Setting.** Products that stop functioning should be replaced as soon as possible, with the failure documented.

6.4 Study Assessments

All study assessments will take place at the times delineated in the Study Events Flow Chart (Table 1) unless otherwise noted below.

Any non-scheduled procedures required for urgent evaluation of safety concerns take precedence over all routine scheduled procedures.

6.4.1 Nicotine Pharmacokinetics

On each of Days 1 through 5, a 4 mL blood sample for plasma nicotine analysis will be drawn into a plastic K₂-EDTA (lavender top) vacutainer tube at the time points delineated in the Study Events Flow Chart (Table 1). Allowable deviation windows for PK sampling are: ± 1 minute for samples collected from 3-60 minutes, and ± 3 minutes for all other samples including the baseline (pre-study product use) sample.

PK blood samples will be collected by direct venepuncture or through an intravenous catheter port as determined by the clinical staff.

Additional blood (typically up to approximately 1 mL) may be drawn between blood draws for the purpose of keeping the needle patent, if required. The blood from the 1 mL draws will be discarded. In total, approximately 300 mL of blood will be drawn from each subject during the entire study for nicotine PK analysis.

The blood samples collected for plasma nicotine analysis may be kept at room temperature prior to centrifugation and will be centrifuged at approximately 1000 to 1300 RCF at $\sim 5^{\circ}\text{C}$ for approximately 10 minutes, within 60 minutes from collection. After centrifugation, the plasma will be transferred to two methanol prewashed 3.5 mL polypropylene screw cap tubes, properly labelled, and then stored at -20°C ($\pm 10^{\circ}\text{C}$) or below (within 120 minutes from collection) until analysis.

Samples will be analysed using a validated liquid chromatography coupled to tandem mass spectrometry detection analytical method with the appropriate quality controls in accordance with FDA Good Laboratory Practice regulations (Title 21 Code of Federal Regulations [CFR] Part 58). Additionally, processing of samples will be completed by a non-tobacco user.

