- l: The number of cigarettes smoked, as appropriate, will be documented from Check-in until beginning of smoking abstinence (Day 1) prior to the start of morning controlled product use on Day 1; Days 1 through 5, 8 hours post morning controlled use session IP start prior to the start of morning controlled product use scheduled on the following day). The number of cigarettes smoked and the number of puffs will be documented during each 4-hour *ad libitum* product use session (Days 1 through 5).
- m: The number of inhalations and reasons for missed puffs will be documented.
- n: To be performed approximately 5 minutes prior to the start of the product use session.
- o: Subjects will be familiarised with the questionnaires. Subjects will receive an explanation of how the questionnaires will be administered and how they will be recorded.
- p: To be performed approximately 10 minutes prior to the start of the product use session.
- q: To be performed approximately 30 seconds prior to the scheduled PK blood draws.
- r: On Days 1 through 5, puff topography measurements will be performed for a 2 hour period during last 2 hours of the 4-hour *ad libitum* product use session. The SPA-M device will need to be reset at 60 minutes as the device can only collect data for approximately 1 hour.
- s: The CRU will attempt to contact all subjects who used at least one study product (including subjects who terminate the study early) approximately 7 days after the final product use to determine if any AE has occurred since the last study visit.

Abbreviations: AE = Adverse event, BMI = Body mass index, BP = Blood pressure, Chem = Serum chemistry, CO = Carbon monoxide, CRU = Clinical research unit, ECG = Electrocardiogram, EOS = End-of-study, FSH = Follicle-stimulating hormone, FU = Follow-up, HBsAg = Hepatitis B surface antigen, HCV = Hepatitis C virus, HIV = Human immunodeficiency virus, HR = Heart rate, HT = Heated tobacco, I/E = Inclusion/exclusion, IP = Inhaled product, PK = Pharmacokinetic(s), RR = Respiratory rate, Scr = Screening, T = Temperature, OBCC = Own brand combustible cigarette

ABBREVIATIONS

| | |
|-----------------------|---|
| AE | Adverse event |
| ANOVA | Analysis of variance |
| AUC | Area under the concentration-time curve |
| AUC ₀₋₉₀ | Area under the nicotine concentration-time curve from time 0 to 90 minutes |
| AUC ₀₋₂₄₀ | Area under the nicotine concentration-time curve from time 0 to 240 minutes |

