HHPs will be used. Subjects will have the opportunity to see the products/devices and packaging and will participate in a Product Trial where they will take 5 puffs on a single one HTP stick (flavour chosen by subject) and 5 puffs on a single HHP stick (flavour chosen by subject). All products/devices used in the trial session will not be used in the clinical study but will be retained as demonstration samples for accountability purposes. An explanation of how the questionnaires will be administered to the subjects will be given. After the familiarisation session and completion of check-in procedures, subjects will be allowed to smoke their own cigarettes *ad libitum* but will abstain from use of any tobacco- or nicotine-containing products for at least 12 hours prior to the start of the morning controlled product use session on Day 1.

In the morning of Days 1 through 5, after pre-use assessments and confirmation of eligibility, subjects will use their randomly-assigned study product under controlled conditions by completely using a single unit (one stick, approximately 10 puffs) of the assigned study product, with puffs taken at 30-second intervals and of 3-second duration. PK samples will be collected within 5 minutes pre-study product use (timepoint '0') and at 2, 4, 6, 8, 10, 15, 30, 45, 60, 120, and 240 minutes following the start of study product use. Questionnaires will be administered to the subject at defined intervals throughout the day. Safety will be monitored throughout the day.

On Days 1 through 5, following the 4-hour PK blood collection, subjects will start a 4-hour *ad libitum* product use session (no limits on cigarette, HTP or HHP consumption) with the same study product used during the morning controlled use session.

On Days 1 through 5, puff topography will be performed over the last 2-hour period during the 4-hour *ad libitum* product use session. The Sodim Smoking Puff Analyzer Mobile (SPA-M) topography device will collect data (puff count, puff duration, puff volume, peak puff flow rate, average puff flow rate, inter-puff interval) for 2 hours. The SPA-M topography device will be reset at 60 minutes in order to collect 2 hours of data.

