7.3.1 Nicotine Pharmacokinetic Analysis

Individual nicotine concentrations will be adjusted for baseline nicotine (“baseline-adjusted”) and all PK parameters will be calculated based on the adjusted concentrations. Baseline adjustment will be performed by subtraction of the pre-existing nicotine concentration from each nicotine concentration obtained after test product administration in that period/day for each subject using the following equation:

$$C_t = C_{t \text{ unadjusted}} - [C_0 \cdot e^{-K_{el} \cdot t_1}]$$

where C_t is the adjusted concentration at time t , $C_{t \text{ unadjusted}}$ is the observed concentration at time t , C_0 is the pre-product use concentration (-5 minutes), $K_{el} \frac{\ln(2)}{t_{1/2}}$, $t_{1/2}$ is 2 hours (average nicotine half-life), t is the actual sampling time since product administration, and t_1 is the actual sampling time since the time of the pre-product use sample. Any resulting negative concentration values following the baseline adjustment will be set to 0.

Nicotine PK parameters will be determined from the adjusted individual subject plasma concentration-time profiles by applying a non-compartmental approach using appropriate validated PK software (e.g., Phoenix[®] WinNonlin[®] version 8.1 or higher).

For each morning product use session on Days 1, through 5, the following PK parameters will be calculated from the baseline-adjusted nicotine concentration-time data:

- | | |
|----------------------|--|
| AUC ₀₋₉₀ | Area under the baseline-adjusted nicotine concentration-time curve from time 0 (defined as the start of the product use session) to the 90-minute time point as calculated by the linear trapezoidal method |
| AUC ₀₋₂₄₀ | Area under the baseline-adjusted nicotine concentration-time curve from time 0 (defined as the start of the product use session) to the 240-minute time point as calculated by the linear trapezoidal method |

| | |
|--------------------|---|
| AUC _t | Area under the baseline-adjusted nicotine concentration-time curve from time 0 (defined as the start of the product use session) to time t. |
| AUC _{inf} | Area under the baseline-adjusted nicotine concentration-time curve from time 0 (defined as the start of the product use session) extrapolated to infinity (represents the total nicotine exposure across time). |
| C _{max} | Maximum baseline-adjusted plasma concentration. |
| C _{last} | Plasma baseline-adjusted nicotine concentration at last time point measured |

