# 8. PHARMACOKINETIC ANALYSIS

#### 8.1 Measurements and Collection Schedule

On each of Days 1 through 5, venous blood samples (~4 mL per sample) for plasma nicotine analysis will be collected within 5 minutes pre-study product use (timepoint '0') and at 2, 4, 6, 8, 10, 15, 30, 45, 60, 120, and 240 minutes following the start of controlled study product use .

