#### 8.3 Pharmacokinetic Concentrations

For the concentration tables, unadjusted plasma nicotine concentrations that are below the limit of quantification (BLQ) will be set to one-half of the lower limit of quantitation for the calculation of descriptive statistics.

Individual nicotine concentrations will be adjusted for baseline nicotine ("baseline-adjusted") and all PK parameters will be calculated based on the adjusted concentrations. Baseline adjustment will be performed by subtraction of the pre-existing nicotine concentration from

each nicotine concentration obtained after test product administration in that period/day for each subject using the following equation:

 $C_t = C_t \text{ unadjusted} - [C_0 \cdot e^{-Kel \cdot t1}]$ 

where Ct is the adjusted concentration at time t, Ct unadjusted is the observed concentration at time t, C0 is the pre-product use concentration (-5 minutes),  $K_{el} = \frac{\ln(2)}{T^{1/2}}$ , T1/2 is 2 hours (average nicotine half-life), t is the actual sampling time since product administration, and t1 is the actual sampling time since the time of the pre-product use sample.

After correction for pre-product administration values, some concentrations may be BLQ and some may be negative values. Negative values will be assigned a value of zero in the analyses and all other values obtained will be reported as is even if these values are BLQ.

Baseline-adjusted plasma nicotine concentrations will be used for the calculation of the plasma nicotine PK parameters.

All concentration data will be included in the calculation of the individual PK parameters, the individual concentration-time plots (based on actual sample times), and in the mean concentration-time plots (based on nominal sample times). However, if there are any significant deviations from nominal sample times, some concentration data may be excluded from the descriptive statistics and the mean concentration-time plots and/or additional concentration-time plots of the mean data may be provided. All deviations and excluded data will be listed and discussed in the CSR.

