# 8.4 Noncompartmental Pharmacokinetic Analysis and Parameter Calculation

The appropriate noncompartmental PK parameters will be calculated from the baselineadjusted plasma nicotine concentration-time data using Phoenix® WinNonlin® Version 8.1 or higher. Actual sample times will be used in the calculations of the PK parameters. The calculation of the actual time for plasma nicotine will be in respect to the start of product use. All PK parameters included in the protocol are listed in Table 8.1 below, and are defined as appropriate for study design.

Parameter	Label to be Used in the Text, Tables and Figures	Definition	Method of Determination
AUC 0-90	AUC0-90	Area under the baseline-adjusted nicotine concentration-time curve from time zero (defined as the start of the product use session) to the 90-minutes time point.	Calculated using the Linear Trapezoidal with Linear Interpolation Method
		If the 90-minutes plasma concentration is missing, BLQ, or not reportable, then interpolation and/or extrapolation will be conducted, as appropriate. If interpolation and/or extrapolation cannot be reliably performed, then this parameter cannot be calculated.	
AUC 0-240	AUC0-240	Area under the baseline-adjusted nicotine concentration-time curve from time zero (defined as the start of the product use session) to the to the 240-minutes time point. If the 240-minutes plasma concentration is missing, BLQ, or not reportable, then interpolation and/or extrapolation will be conducted, as appropriate. If interpolation and/or extrapolation cannot be reliably performed, then this parameter cannot be calculated.	Calculated using the Linear Trapezoidal with Linear Interpolation Method
AUCt	AUCt	Area under the baseline-adjusted nicotine concentration-time curve from time zero (defined as the start of the product use session) to the time of the last measurable non-zero concentration.	Calculated using the Linear Trapezoidal with Linear Interpolation Method
AUC inf	AUCinf	Area under the baseline-adjusted concentration-time curve from time 0 extrapolated to infinity	Calculated as: $AUC_t + (C_{last}/ K_{el})$ where $C_{last}$ is the last observed/measured concentration

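### Protocol 6.4.1 leaves the scheduled 2-minute PK sample out of the ±1 minute window, so it gets ±3 minutes, which can blur the first uptake point if staff use it

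*Protocol*

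**What the plan says.** Protocol 6.4.1 allows ± "1 minute for samples collected from 3-60 minutes, and ± 3 minutes for all other samples including the baseline (pre-study product use) sample". SAP 8.1 schedules blood draws before use "and at 2, 4, 6, 8, 10, 15, 30, 45, 60, 120, and 240 minutes following the start of controlled study product use". Protocol 3.1 and the synopsis give the same times.

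The sampling times are then used in two ways:

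- **Actual times.** SAP 8.4 states: "Actual sample times will be used in the calculations of the PK parameters". SAP 8.3 also uses actual times for the individual plots and in the baseline-adjustment formula.
- **Nominal times.** SAP 8.3 draws the mean plots on nominal times. SAP 8.5 computes mean, SD, CV% and SEM at each nominal time for unadjusted and baseline-adjusted concentrations, and presents the linear mean plots with and without SD.

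SAP 8.3 also allows concentrations to be left out of the descriptive statistics and mean plots when sample times depart significantly from nominal. It adds: "All deviations and excluded data will be listed and discussed in the CSR".

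**The concern.** The lower limit of the tight window, 3 minutes, matches no scheduled sample. The 2-minute draw is the only post-use sample in the first hour that misses the ±1 minute rule, and it falls while the product is still being used and concentration should be climbing. It has the same tolerance as the 240-minute sample, and that tolerance exceeds its own nominal time. Nothing in the documents suggests that this was deliberate. The 4- and 8-minute draws, each with an Urge to Smoke questionnaire just beforehand, are held to ±1 minute, while the 2-minute draw has no questionnaire attached.

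At stake is how precisely the first uptake point is described in the concentration tables and the mean (SD) figures (SAP 14.2.2). A draw at 4.5 minutes would comply with the protocol and could be tabulated and plotted as a 2-minute value.

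**Working it through.** **Inputs from the documents.** Windows: Protocol 6.4.1. Sampling times: SAP 8.1. Puffing: about 10 puffs, 30 seconds apart (Protocol 6.3). Sample size: 25. The plan states no figure of its own on this point.

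**Assumptions, not in the documents.** Concentration rises linearly from zero at the start of use and is still rising at 5 minutes, so C is proportional to max(0, t). Draw-time distributions and between-subject CV are also assumed.

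**Step 1: windows.** 2 min ± 3 gives -1 to +5; 4 min ± 1 gives +3 to +5; 6 min ± 1 gives +5 to +7. The 2-minute window contains the whole 4-minute window. With ±1 minute it would be +1 to +3.

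**Step 2: puffs started by time t** = min(10, floor(t/0.5) + 1), with the first puff at time 0. Results: 1 at 0 min, 3 at 1 min, 5 at 2 min, 7 at 3 min, 10 at 5 min. The present window spans 1 to 10 puffs (none if drawn before the start); ±1 minute would span 3 to 7.

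**Step 3: timing-only CV, draws evenly spread.**

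| Draw range (min) | Mean of max(0, t) | SD | CV |
|---|---|---|---|
| +1 to +3 | 2 | 2/√12 = 0.577 | 29% |
| 0 to +5 | 2.5 | 5/√12 = 1.443 | 58% |
| 0 to +5, and before the 4-minute draw | 2.042 | 1.224 | 60% |
| -1 to +5 | (25/2)/6 = 2.083 | √((125/3)/6 - 2.083²) = 1.614 | 77% |

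In the third row the 4-minute draw is evenly spread over +3 to +5. Dividing by √25 = 5, the SEM is about 12-15% of the mean, against about 6% with ±1 minute. The mean moves by +4% over -1 to +5 and by +2% when the draw must precede the 4-minute sample. It would move by +25% only if draws ran evenly over 0 to +5 regardless of the 4-minute draw.

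**Step 4: draws clustered at 2 minutes (triangular).** The CV is 59% over -1 to +5 and 52% when cut at 0, against 0.408/2 = 20% with ±1 minute.

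**Step 5: adding between-subject variation.** Combined CV = √((1 + CVb²)(1 + CVt²) - 1). With an assumed CVb of 50% and even spread over 0 to +5: √(1.25 × 1.333 - 1) = 82%. With ±1 minute: √(1.25 × 1.083 - 1) = 60%. For CVb of 75% and 100% the pairs are 104% against 83%, and 129% against 108%.

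**Step 6: residual nicotine.** The zero start suits the baseline-adjusted output. Unadjusted values carry pre-existing nicotine. If that equals the 2-minute rise (an assumption), 58% becomes 1.443/(2.5 + 2) = 32%, and 29% becomes 0.577/(2 + 2) = 14%.

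**Step 7: primary parameters.** Take a linear rise to 5 minutes and a 120-minute half-life afterwards. Moving the 2-minute draw anywhere from -1 to +5 then changes AUC to 240 minutes by 0 to 0.08% when actual times are used.

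**The case against.** **A tolerance is not scatter.** Spread appears only if staff use the allowance. If the 2-minute draw is taken as tightly as the ±1 minute draws, nothing is added (29% against 29%). This stands, so the effect is a possibility and its size an illustration.

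**The schedule limits drift.** A questionnaire is due about 30 seconds before the 4-minute draw (Table 1 footnote q), and that draw has ±1 minute. A 2-minute draw at +5 would run past both. This makes the extremes less likely. It is not a bar, because the questionnaire has its own ±2 minute tolerance (Protocol 6.4.2), and requiring the draw to precede the 4-minute sample still gives 60%.

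**The window might refer to actual collection time.** A 2-minute sample taken after 3 minutes would then be out of window. That reading is strained, because it classifies a sample by the quantity that the window is meant to judge. It would also leave 0 to +3 open, where even spread gives 0.866/1.5 = 58%.

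**Safeguards exist.** SAP 8.3 ties exclusion to departures from nominal time rather than to protocol windows, and the blood-draw listing shows elapsed time for each sample. Both help. But exclusion is discretionary and has no threshold, and a draw within the protocol window would not clearly trigger it.

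**Stronger readings.** A reader might infer that the primary comparisons are compromised. The documents do not support this: Cmax and AUCt use actual times, SAP 8.6 does not test the 2-minute concentration, and nothing suggests that draw timing differs by product. A reader might also make something of the baseline wording. Table 1 footnote n says "To be performed approximately 5 minutes prior to the start of the product use session", which with ±3 minutes gives -8 to -2, whereas Protocol 3.1 and SAP 8.1 require the sample in the last 5 minutes. Because the adjustment uses the actual interval, the share of the pre-use value subtracted at 8 minutes is exp(-ln2 × 16/120) = 0.91 to exp(-ln2 × 10/120) = 0.94, which is immaterial.

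**Conclusion.** The gap between the window rule and the schedule is real on the plain reading of Protocol 6.4.1. Its consequence is conditional and descriptive. If draws use the ±3 minutes, the spread displayed at the nominal 2-minute point can widen. Timing-only CV is up to about 58-77% against 29% with ±1 minute, given evenly spread draws and a linear rise from zero. It is lower with residual nicotine and shows no increase if draws stay near 2 minutes. The wording gap is certain; the CVs depend on an assumed curve and assumed draw times. No effect on the primary analysis and no bias in product ratios is shown. Minor, but worth correcting because it changes how one sample is collected.

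**What to change.** In Protocol 6.4.1, apply ±1 minute to samples scheduled from 2 to 60 minutes and ±3 minutes to the samples scheduled at 120 and 240 minutes. Keep a stated tolerance for the pre-use sample, so that the rewritten sentence does not drop it.

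The cost is one sentence and probably a few more logged timing deviations at the 2-minute draw. No analysis, sample-size or SAP exclusion-rule change is needed.

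Separately, and as an editorial matter only, the pre-use sample timing could be given the same wording throughout: Protocol synopsis, sections 3.1, 6.4.1 and 7.3.1, and Table 1 footnote n; SAP sections 3, 8.1 and 8.3.
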